14.0 Risks to Participants

For each risk or set of risks below, include the procedures to be performed to lessen the probability, magnitude, duration, or reversibility of those risks.

1. Foreseeable Risks: Although unlikely, there is a possible risk of knowledge of genetic information. Given that none of the genes we are assessing are severe disease causing genes we find this highly unlikely.
2. Reproduction Risks: N/A
3. Risks to Others: It is possible that family members will try to infer their genetic results based on those of the participant.

15.0 Potential Benefits to Participants

1. Potential Benefits: There are no direct benefits to the participants.

16.0 Data Management

1. Data Analysis Plan:

The Investigator is responsible to ensure the accuracy, completeness, and timeliness of reported data.

PROTOCOL TITLE:

VERSION DATE:

All data will be compiled within the Fairview system on secure servers. De-identified final data may be sent to Geneticure using a secure, password-protected Excel spreadsheet on a server that is only accessible to IRB-approved personnel and is fully auditable. The database will be validated prior to use in the study. All required data will be recorded on CRFs or paper facsimiles. Data collected within the CRFs will be supported by source documents as appropriate and may be updated to reflect the latest observations on the subjects participating in the study. Corrections to the source documentation will be made in a manner that does not obscure the original entry and will be dated and initialed by the Investigator or assigned designee. It is important for data entry to occur in a timely manner, therefore, data collected on source documents should be transferred into CRFs as soon as possible following study visits.

All data will be coded for statistical analysis (i.e. drug classes will be coded numerically and genotypes will be coded numerically). Subject's raw genetic data will be entered into the Geneticure for Hypertension algorithm. All data will be analyzed with SPSS v.20. Normality of the data will be assessed using Levene's test prior to statistical analysis and any correction for non-normal data distribution will be used. Descriptive statistics will be computed (average time for blood pressure control, average number of visits to the clinician for blood pressure control, age, height, weight, BMI, etc.).

Data will be initially analysed following the collection of samples/data from up to 600 subjects. Statistical tests will be corrected for the number of tests run (preservation of alpha). Ordinary least squares regression via univariate modelling will be used to estimate the magnitude of linearity between drug class that yielded the best blood pressure control and genetic profile of the subject. Multiple regression analysis will be performed to determine the impact of confounding variables (height, weight, age, race) on blood pressure control. For all statistical analyses an alpha level of 0.05 will be used to determine statistical significance.

Missing Data

All patients with available data will be included in the analyses of the study objectives. No patients will be directly contacted to retrieve missing data, and no sensitivity analyses will be performed on missing data.

2. Power Analysis:

Power Calculation and Sample Size:

Given the unique study design and pilot/feasibility nature of this proposal, highly accurate preliminary data are not available to generate detailed power calculations on the impact of the Geneticure panel for hypertension therapy. This is due to the lack of studies that have been performed in a prospective manner on genetic guidance for hypertension. However, previous work from our group utilizing a relatively small sample size and chart review have yielded data on all

PROTOCOL TITLE:

VERSION DATE:

17 genes that are contained within the Geneticure panel for hypertension treatment. Several of the genes with large effects can demonstrate statistical differences at relatively small sample sizes. For instance position 49 of the beta-1 adrenergic receptor demonstrates a functional genotype mean arterial blood pressure of 97mmHg (SD of 12.4mmHg) with beta-blocker therapy and the non-functional genotype demonstrates a mean arterial blood pressure of 102mmHg (SD of 11.5mmHg) with this same therapy. A power calculation based on this site of the beta-1 adrenergic receptor would yield a sample size per group needed of 109 for an alpha level of 0.05 and a power of 0.80 (not correcting for multiple comparisons) (table 1). Based on these results we can determine that the gene with the smallest effect from this previous smaller study (specifically that encoding WNK-1, rs2107614) will determine the approximate sample size needed to observe an effect, if an effect exists, for the panel as a whole in this prospective trial. Data from our phase-I trial demonstrates a mean arterial blood pressure of 97.6mmHg with diuretic therapy in the functional genotype group of WNK-1 and a mean arterial blood pressure of 100.8mmHg (Pooled SD = 12) with diuretic therapy in the non-functional genotype group for this site of WNK-1. Without correcting for multiple comparisons, one can determine that a per-group sample size of 162 individuals would be needed for 80% power with an alpha of 0.01. Using an alpha of 0.05 and a power of 0.80 we have estimated that we will need 300 subjects per group to observe a significant difference, where one exists. Based on possible retention of 70% of subjects who initially enroll, we will seek to recruit up to 2000 subjects for the study.

Concomitant Medications/Treatment/Procedures

This study protocol does not require change to any existing treatments or those prescribed during the course of the study by the Investigator or any other provider whom the subject sees for any medical reason. Outside of eligibility screening, there are no clinical evaluations planned as part of this study.

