3.0 Study Endpoints/Events/Outcomes

1. Primary Endpoint/Event/Outcome:

To assess the effectiveness of the use of a patient’s genes to predict which hypertension therapy is successful, as measured by:

1. Level of blood pressure control (<140/<90)
2. Change in blood pressure from baseline to control

2. Secondary Endpoint(s)/Event(s)/Outcome(s):

Blood Pressure control with respect to:

1. Number of medications needed to obtain control
2. Time to control
3. Number of office visits to control
4. Side effects from hypertension therapy
5. Hypertension associated adverse events during the course of treatment

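### The plan checks normality with Levene's test, which compares variances and not shape, so the trigger for its non-normality correction answers the wrong question; the effect on inference is modest

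*Combined protocol and SAP*

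**What the plan says.** The data analysis plan in section 16.0 (Data Management) of the combined protocol and SAP gives one instruction on distributions: "Normality of the data will be assessed using Levene's test prior to statistical analysis and any correction for non-normal data distribution will be used". It does not say which groups the test would compare, which form of the test is meant, or what the correction would be. The significance rule is general: "For all statistical analyses an alpha level of 0.05 will be used to determine statistical significance".

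The modelling text that follows is short. For the genetic association it says "Ordinary least squares regression via univariate modelling will be used to estimate the magnitude of linearity between drug class" and genetic profile, and it adds a multiple regression for confounders of blood pressure control. Time and visits appear in this section only among the descriptive summaries ("average time for blood pressure control, average number of visits to the clinician for blood pressure control"). Section 3.0 lists both as secondary outcomes, together with "Number of medications needed to obtain control", but section 16.0 assigns none of the three a model.

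No section names a Q-Q plot, a residual check or a formal test of shape. Equality of variance, which Levene's test does address, is not mentioned anywhere.

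**The concern.** The sentence refers to normality at its start and to non-normal data at its end, so it cannot be read as a variance check loosely worded. It makes a test of spread the gate for a correction of shape. Such a gate can err in two directions. Skewed data with the same spread in each group satisfy Levene's null hypothesis and tend to pass. Normal data with different spread violate it and can be sent for a correction they do not need, while the unequal variance that was actually detected has no stated remedy.

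At stake is the scale on which outcomes are analysed. That choice would rest on a test that does not bear on it, and because the correction is unspecified it would be made after the data are seen.

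**Working it through.** The plan gives no figure on this point, so there is nothing to reproduce. The check is of what the named test responds to.

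**Inputs from the plan (section 16.0)**
- Cut-off 0.05.
- Group size 300: "we have estimated that we will need 300 subjects per group to observe a significant difference, where one exists".
- Pilot SDs for position 49 of the beta-1 adrenergic receptor: 12.4 mmHg ("mean arterial blood pressure of 97mmHg (SD of 12.4mmHg) with beta-blocker therapy") and 11.5 mmHg in the non-functional genotype.
- WNK-1 planning effect: means 97.6 and 100.8 mmHg, pooled SD 12, so (100.8 − 97.6)/12 = 3.2/12 = 0.267 SD.

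**Assumed, because the plan is silent:** two genotype groups as the grouping, the skewed shapes and their log-SDs, the SD pair 12 and 15, and the use of 0.267 for outcomes other than blood pressure.

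**The test.** Let z_ij = |y_ij − centre of group i|, with the group mean or median as centre. Levene's statistic is the one-way analysis-of-variance F on z:

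W = [(N − k)/(k − 1)] × Σ n_i (z̄_i − z̄)² / ΣΣ (z_ij − z̄_i)²

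Here N = 600 and k = 2, so W is referred to F(1, 598). It compares average absolute deviation between groups. Two groups with the same distribution, however skewed, satisfy its null hypothesis.

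**Step 1: share of data sets flagged (two groups of 300, 4,000 runs)**

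| Data | Levene, mean-centred | Levene, median-centred | Shapiro-Wilk on residuals |
|---|---|---|---|
| Lognormal, log-SD 0.5, identical groups | 9.7% | 4.9% | 100% |
| Lognormal, log-SD 1.0, identical groups | 17.7% | 3.9% | 100% |
| Exponential, identical groups | 12.5% | 4.9% | 100% |
| Gamma (shape 4), identical groups | 7.5% | 4.8% | 100% |
| Skewed count, identical groups | 8.1% | 5.4% | 100% |
| Normal, equal SD | 4.5% | 4.6% | 5.1% |
| Normal, SD 12.4 and 11.5 (plan) | 23.7% | 23.5% | 5.8% |
| Normal, SD 12 and 15 (assumed) | 94.7% | 94.5% | 9.2% |

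The lowest pass rate for skewed data is 100 − 17.7 = 82.3%, and the highest is 100 − 3.9 = 96.1%. Repeat simulations put the plan's own SD pair at about 22–24%. With 109 per group that pair is flagged in 11–12% of runs, and the skewed shapes in 8–19% (mean-centred) or about 5% (median-centred).

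**Step 2: when the groups differ.** For lognormal data with log-SD σ and a shift of 0.267σ on the log scale, the ratio of raw SDs is exp(0.267σ): 1.14, 1.24 and 1.31 for σ = 0.5, 0.8 and 1.0. The effect itself therefore creates unequal variance, and Levene's test flags about 38–64% of these data sets, depending on σ and the form of the test. Whether a correction is triggered then depends partly on the effect under study.

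**Step 3: consequence for inference (two-sided tests, 300 per group)**
- Type I error of the raw-scale t-test: lognormal with log-SD 0.5, 0.8 and 1.0, 4.7%, 5.3% and 4.4%; exponential, 4.6%; normal with SDs 12.4 and 11.5, 5.2%.
- Blood pressure, means 97.6 and 100.8, SDs 12.4 and 11.5: power 91% by t-test, 89% by Mann-Whitney, 92% by t-test on logs. A needless correction costs at most 91 − 89 = 2 points under these two choices.
- Lognormal outcome with a 0.267 SD shift on the log scale: raw-scale power about 87%, 79% and 72% for log-SD 0.5, 0.8 and 1.0, against about 90% on the log scale.

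**The case against.** The strongest reply accepts that Levene's test is the wrong tool and disputes that it matters. Most of that reply stands.

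- **False positives.** A reader might infer that undetected skew makes the significance tests invalid. Step 3 does not support this: with 300 per group, type I error stays near 5%.
- **Always or never.** A reader might also infer that skewed outcomes always pass and that unequal spread is always corrected. Neither is so. The mean-centred form flags about 7–18% of identical skewed groups, and about 76–78% of normal data sets with the plan's own SDs are left alone. The high flag rate at SDs 12 and 15 belongs to an assumed pair; 12.4 and 11.5 is the only unequal pair the plan reports.
- **Secondary outcomes.** It is tempting to say that time, visits and medication counts will be analysed by least squares on the raw scale. Section 16.0 does not say so. It ties least squares to drug class and genetic profile, and multiple regression to blood pressure control. The absence of a model for these outcomes is a separate gap, which replacing Levene's test would not close.
- **Power comparison.** Exactly lognormal data with a constant log shift favour the log scale by construction, and 0.267 is borrowed from a blood pressure effect. The range of 72–87% is an illustration. Only log-SD 1.0 falls clearly below the plan's 80% target.

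The reply does not rescue the sentence. No other text supplies a check of shape, and calling the study pilot work does not make a variance test a normality test.

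**Conclusion.** The instruction is wrong as written: it cannot do what it says, and nothing elsewhere in the plan corrects it. Its consequence is modest, so this is a correction to make when the analysis text is next revised, and not a defect that undermines the study.

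The misdirection of the gate follows from the definition of the test and needs no assumption. The flag rates rest on two equal groups of 300, a 0.05 cut-off and, for skewed data, assumed shapes. For blood pressure the harm is close to nil. For time to control, visits and number of medications a real loss of power is possible, but it depends on a raw-scale least-squares analysis that is inferred and on distributions that the documents do not describe. The open-ended correction adds some analytic freedom, which is reason enough to fix the wording before data are analysed.

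**What to change.** Replace the sentence in section 16.0 with wording such as:

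> *Distributional assumptions will be judged on model residuals (Q-Q plots). Levene's test will be used only to check equality of variance; where variances differ, Welch or heteroscedasticity-robust standard errors will be used.*

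Then state in advance the scale or model for each time and count outcome (for example a log scale or time-to-event model for time to control, and a count or rank-based method for visits and medications), so that the choice does not depend on a pre-test. A plot is preferable to a formal normality test as the main guide, because with about 600 subjects a formal test will also flag minor departures.

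The cost is a few sentences of analysis text, with no new data and no burden on participants. The plan says "All data will be analyzed with SPSS v.20", so the team should confirm that robust standard errors can be obtained in that version, or name the software that will supply them.

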Secondary Objective(s)	
1. Number of medications needed to obtain control2. Time to control3. Number of office visits to control4. Side effects from hypertension therapy5. Hypertension associated adverse events during the course of treatment
Research Intervention(s)/Investigational Agents	Association between blood pressure control and genetic variants important in blood pressure regulation.
IND/IDE # (if applicable)	
Investigational Drug Services # (if applicable)	
Study Population	Hypertensive patients who have achieved BP control
Sample Size (number of participants)	Up to 2000
Study Duration for Individual Participants	Less than one day

PROTOCOL TITLE:

VERSION DATE:

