Unfortunately, despite a significant impulse in the medical community to move towards an "individualized medicine" approach to patient centered treatment, the current clinical treatment strategy is based on a set algorithm which does not take into account individual patient differences. Rather, physicians are guided to choose a drug (one out of many options) in a given class of drugs and use that specific drug as a "first line therapy" (typically initiating with the diuretic class) and titrate that specific drug of choice to therapeutic dosage regardless of efficacy². It is only after a prolonged course of treatment with that specific class of drug that clinical efficacy is determined (typically three months). At this stage, if clinical guideline goals for blood pressure have not been met, it is often recommended that the patient remain on the "first line therapy" whilst an additional drug from a different class of drugs (typically an Angiotensin converting enzyme inhibitor (ACE inhibitor) or Angiotensin II receptor blocker (ARB)) is added to the

PROTOCOL TITLE:**VERSION DATE:**

pharmacologic regimen. Again, this drug is titrated to recommended therapeutic dosage and another prolonged course of treatment is initiated before clinical efficacy is determined (an additional three months – six months since initiation of treatment). If at this point, clinical guideline goals for blood pressure have not been met, a third drug from a third class of drugs (typically a beta-blocker) is added and the process is repeated (another three months – nine months from initiation of treatment). Further, if clinical guideline goals have continued to be elusive, the diagnosis of refractory hypertension is added and the process is reinitiated with a different combination of drugs, different classes of drugs, different drug options within a given class of drugs, different dosages, or all of the above. Thus, from the time of initial diagnosis and the start of treatment to the point in which blood pressure is adequately controlled may take anywhere from three months to well over one year. This trial-and-error standard of care is clearly not optimal.

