4.0 Study Intervention(s)/Investigational Agent(s)

1. Description: A multigene panel comprised of genes with known functionality in the heart, vasculature, and kidney, that are known to influence BP. This study will be performed as a retrospective study on patients within the Fairview Health System. Patients will be those who have been previously diagnosed with hypertension and have a history of blood pressure control (<140/<90 for two consecutive office measures. The study will involve collection of a buccal swab (can be done at the patient’s home, by the patient) and a clinical chart review of the patient’s hypertension and medication history. From the buccal swab we will assess 18 SNPs in 11 genes (2) SNPs in ADRB1, (2)

PROTOCOL TITLE:

VERSION DATE:

SNPs in ADRB2, (1) in SCNN1A, (1) in ADD1, (2) in SLC12A3, (3) in WNK1, (1) in ACE, (3) in AGT, and (1) each in AGTR1, CYP2D6*4 and REN) with known functionality in the liver, heart, vasculature, and kidney.

2. Drug/Device Handling: The device used for sample collection is a buccal swab kit that gently removes cells from the inside of the cheek. The Geneticure kit contains two buccal brushes and two tubes of lysis buffer. The patient swabs their left cheek and deposits the end of the swab in the lysis buffer, then does the same for the right cheek. This swab is placed (by the patient) in lysis buffer (a small tube) and shipped to the study site, if collected off site. The swab is then shipped to the University of Arizona Genomics core facility for DNA extraction, quantification, and assessment of the genes listed above. The study is retrospective in nature and the DNA assessment will not influence prescribing, i.e. no drugs will be changed based on this analysis for the patients. No identifying information will EVER accompany the kit to the genetic testing facility.
3. IND/IDE: In-vitro diagnostic device and exempt from IDE.
4. Biosafety: N/A

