9.0 Study Population

1. Inclusion Criteria:
 1. Subject is able and willing to provide informed consent
 2. Subject is ≥ 20 and ≤ 85 years of age

PROTOCOL TITLE:

VERSION DATE:

3. Subject with diagnosis of Hypertension for a minimum of 1 year
4. Subject has been on the same class/classes of blood pressure medication for a minimum of 6 months. Note: A change in dosage, frequency, or specific medication is acceptable as long as there have been no changes to the class/classes of medications prescribed.
5. Subject with a Body Mass Index (BMI) ≥ 19 and ≤ 45
6. Subject is currently prescribed and taking one of the following classes of medications alone or in combination with each other.
 - o Diuretics (thiazide or thiazide-like)
 - o ACE Inhibitors
 - o Angiotensin Receptor Blocker (ARB)
 - o Beta-blockers
 - o Ca+ Channel Blockers

2. Exclusion Criteria:

1. Subject has a diagnosis of secondary hypertension or is experiencing a complication of pregnancy.
2. Subject is currently prescribed and taking any additional class of medication(s) for high blood pressure not included in the list above
3. Subject has Systolic BP > 190 or Diastolic BP > 120 documented within the six months prior to visit.
4. Any other reason that the subject is inappropriate for study enrollment in the opinion of the Investigator.

2. Screening:

Because this is a retrospective chart review study, subjects will be screened by a Fairview employee (or AHC personnel) for eligibility. Only subjects who have opted in (or who have not opted out) of research will be contacted.

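### Time and visits to control have only pooled averages as their analysis, with no genetic comparison and no rule for never-controlled patients, whom the eligibility list lets in

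*Combined protocol and SAP*

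**What the plan says.** Section 3.0 lists "Time to control" and "Number of office visits to control" among the secondary outcomes. The Data Analysis Plan in section 16.0 mentions them once, in a list of descriptive statistics that also covers age, body size and the like: "average time for blood pressure control, average number of visits to the clinician for blood pressure control". No split by genotype or by algorithm recommendation is given. The inferential methods named there are a least-squares regression relating drug class to genetic profile and a multiple regression for blood pressure control. Neither concerns time or visits.

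The missing-data paragraph of section 16.0 analyses whoever has data and rules out sensitivity analyses for missing values.

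On who is in the sample, the documents differ:

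- The Study Summary gives the population as "Hypertensive patients who have achieved BP control".
- Section 4.0 says that patients "have a history of blood pressure control (<140/<90 for two consecutive office measures".
- Section 9.0 has no control criterion. The nearest is treatment stability: "Subject has been on the same class/classes of blood pressure medication for a minimum of 6 months". Its blood pressure exclusion applies only above 190 systolic or 120 diastolic.
- Section 5.0 (Screening) refers staff to the inclusion and exclusion sections as the full set of criteria.

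**The concern.** There are two separate problems.

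First, a single average over all patients says nothing about whether genes predict how quickly, or in how many visits, control is reached. That holds whoever is enrolled.

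Second, a patient who has not reached control has no time to control, only a lower bound. An average over available values leaves that patient out, so it describes only those who succeeded. If the same averages were later split by genetic match, the group with more failures would lose more of its slow patients, and the comparison would be distorted. The protocol's own background makes this plausible, since it says that reaching control "may take anywhere from three months to well over one year".

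**Working it through.** The plan gives no effect size, standard deviation, event count or sample size for time or visits to control, so there is no figure of its own to reproduce. The check is a comparison of passages followed by an illustration on assumed inputs.

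**Can a never-controlled patient enrol?** Take a treated patient diagnosed more than a year ago, on an unchanged listed drug class for over six months, with readings around 160/100 throughout and the other criteria met. Section 9.0 admits this patient, since 160 is below 190 and 100 is below 120. The Study Summary and section 4.0 do not. Level of control is also a primary outcome in section 3.0, and it would carry little information if everyone had reached control. The documents therefore conflict, and the list that screening staff are told to use is the permissive one.

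**What happens to the average time?** Assume exponential times to control with true mean m, and a chart look-back of W months. The average among those controlled within W is

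m − W·e^(−W/m) / (1 − e^(−W/m)),

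and the share left out is e^(−W/m). For W = 12:

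- m = 6: 6 − 12 × 0.1353/0.8647 = 4.12 months, with 13.5% left out.
- m = 12: 12 − 12 × 0.3679/0.6321 = 5.02 months, with 36.8% left out.

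The true difference is 6 months. The observed differences below come from unrounded means.

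| Look-back W (months) | Averages seen | Difference seen | Share of true difference |
|---|---|---|---|
| 12 | 4.12 v 5.02 | 0.89 | 15% |
| 24 | 5.55 v 8.24 | 2.69 | 45% |
| 36 | 5.91 v 10.11 | 4.20 | 70% |
| 60 | 6.00 v 11.59 | 5.60 | 93% |

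With true means of 6 and 9 months the shares are 19%, 55%, 81% and 98%. The means, the exponential shape and the windows are all assumptions. Section 5.0 says that data are collected for up to one year, but not whether that is a chart look-back.

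**What happens to visits?** Assume that the chance of control at each visit is 0.50 in one group and 0.35 in the other, with at most K visits on record. The true means are 1/0.50 = 2.00 and 1/0.35 = 2.86, a difference of 0.86. The average among the controlled is Σk·p(1−p)^(k−1) / Σp(1−p)^(k−1), summed over k = 1 to K. This gives differences of 0.25 (K = 4), 0.63 (K = 8) and 0.85 (K = 20).

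**Is the direction fixed?** No. Suppose that in group A 60% are controlled at a mean of 4 months, 30% at a mean of 15 months, and 10% never. In group B 60% are controlled at a mean of 4 months and 40% never. The average among the controlled is (0.6 × 4 + 0.3 × 15)/0.9 = 7.7 months in A and 4.0 in B. Group B does worse but looks faster.

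**The case against.** The strongest reply is that two places in the protocol restrict the sample to patients who have reached control. On that reading every subject has a time to control, nobody is censored, and the average leaves nobody out. Any bias then arises from selection at entry, which Kaplan-Meier or Cox methods on the enrolled sample cannot undo. This stands for that reading. The 190/120 exclusion does not settle the matter either, because a patient above 140/90 today may have been controlled earlier. What it does not answer is that section 9.0, presented as the complete list, contains no such restriction.

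A reader might infer that the planned averages shrink real differences between groups. The documents do not support that. The averages are pooled, no group contrast of them is planned, the loss is close to nil with a long look-back, and the order can reverse.

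Two points about the remedy also stand. A negative binomial model with a follow-up offset estimates visits per unit of time, which is a different quantity from visits to control. And if algorithm match were judged on the current regimen, which section 9.0 requires to have been stable for six months, exposure would be fixed after time zero and would build in immortal time.

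Finally, these are secondary outcomes in what section 16.0 calls a pilot or feasibility proposal. That limits the weight of the point, but the change is small.

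**Conclusion.** The concern holds in a limited form. On any reading of the population, no analysis is specified that relates time or visits to control to genetics, although both are listed outcomes of a study about genetic prediction. If section 9.0 governs, never-controlled patients can enter and would fall out of the averages, so the results would be conditional on success. A comparison built on them would be biased, often but not always toward no difference.

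The size cannot be computed from the documents. On the assumed exponential times (6 v 12 and 6 v 9 months), between 15% and 98% of the true difference survives as the look-back goes from 12 to 60 months. If every enrolled patient reached control and the full history is captured, the averages leave nobody out; what remains is the missing genetic comparison and the need to state that the results are conditional on control.

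**What to change.** 1. Reconcile the Study Summary and section 4.0 with section 9.0 on whether a history of control is required for entry.
2. Define time zero as the first antihypertensive prescription. Take as the event the protocol's own control definition (two office readings in a row below 140/90), and say which of the two readings dates it. State the look-back window, and censor at the last blood pressure in the chart.
3. Replace the average time with Kaplan-Meier estimates and a log-rank or Cox comparison by algorithm match, with the match defined on the regimen prescribed at time zero.
4. Analyse visits to control with the same censoring on the visit-number scale, using a discrete-time model, not a rate model with a follow-up offset.
5. Report the proportion controlled in each group.
6. If only controlled patients are eligible, state that time and visits are conditional on having reached control, and that censoring methods cannot restore patients excluded at entry.

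The cost is modest: revised wording, some extra analysis, and abstraction of first-prescription and reading dates. Dates of this kind are needed to compute time to control in any case. Whether the chart-review form already captures them could not be checked, because the attachment listing the additional data items is not part of the documents.
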